The primary variables will be summarized for the SAF by treatment group in terms of the number of patients experiencing a treatment emergent AE, as well as the exposure-adjusted incidence rate (patients with treatment emergent AEs per patient year of follow-up to first event [AE or censoring]). The duration of on-treatment follow-up in years will be calculated for each patient as (treatment end date - treatment start date + 2 days)/365.25 without taking into account treatment interruptions. Summaries of the other primary variables, treatment emergent SAEs and AEs leading to study treatment discontinuation, will be similarly presented. Additionally, incidence rates may be compared with epidemiological background rates in appropriately matched populations.

Estimates of the cumulative incidence of the primary outcomes will be displayed graphically for the SAF.

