While no formal hypothesis testing is foreseen for the primary safety objectives, if both QAW039 doses have a 50% relative hazard increase for treatment emergent events, compared with placebo, then there will be approximately > 99%, 94% and 38% power that the two-sided 95% confidence interval not adjusted for multiplicity for one of the two QAW039 doses would exclude no effect for the primary safety variables of time-to-first treatment emergent AE, time-to-first treatment emergent SAE, and time-to-first treatment emergent AE leading to study treatment discontinuation analyzed across Treatment Period 1 and Treatment 2 combined, respectively. The power was estimated using 10,000 simulations based on 1,570 patients being randomized into the current study. In addition, the sensitivity of the power is further assessed for different scenarios of sample size (1470 patients and 1670 patients). This power will be higher, if more patients are randomized (e.g., due to additional new patients being enrolled) or more patients completing prior Phase 3 studies of QAW039 elect to participate in the current study.

The underlying assumptions for the power simulations were an exponential censoring rate in the placebo group of 0.22 and of 0.16 in the QAW039 treatment groups. The assumptions on the exponential event rate in each treatment group are shown in [Table 9-1](#). These assumptions are based on the, DREAM ([Pavord et al. 2012](#)) and MENSA ([Ortega et al. 2014](#)) trials, as well as a QAW039 Phase 2 study in moderate-to-severe asthma. The detailed power calculations are shown in the [Table 9-2](#) and [Table 9-3](#).

Table 9-1 Assumed placebo event rates for power calculations

Endpoint	Previous study patients were enrolled in or new patients	Assumed exponential event rate (per patient-year)
Rate of AEs	QAW039A2316/ QAW039A2317	3.01
	QAW039A2307/ QAW039A2314	2.86
	New patients	2.86
Rate of SAEs	QAW039A2316/ QAW039A2317	0.07
	QAW039A2307/ QAW039A2314	0.24
	New patients	0.24
Rate of AEs leading to study treatment discontinuation	QAW039A2316/ QAW039A2317	0.03
	QAW039A2307/ QAW039A2314	0.03
	New patients	0.03

Table 9-2 Power (%) for a non-multiplicity adjusted confidence interval to exclude no-difference versus placebo for the primary safety variables

Primary Endpoint	Treatment Period	QAW039 150 mg versus placebo	QAW39 450 mg versus placebo	Both QAW039 150 mg and 450 mg versus placebo	One of the two QAW039 doses versus placebo
Time-to-first AE	1	>99	>99	>99	>99

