2.5 Analysis of the primary objective

2.5.1 Primary endpoint

Primary endpoints for the study are:

Treatment Period 1:

- Time-to-first treatment emergent adverse events (AEs);
- Time-to-first treatment emergent serious adverse events (SAEs); and
- Time-to-first treatment emergent AE leading to discontinuation from study treatment.

of QAW039 (150 mg once daily and 450 mg once daily), compared with placebo in patients with moderate-to-severe asthma receiving SoC asthma therapy.

Treatment Period 1 and Treatment Period 2 combined:

- Time-to-first treatment emergent adverse events (AEs);
- Time-to-first treatment emergent serious adverse events (SAEs); and
- Time-to-first treatment emergent AE leading to discontinuation from study treatment.

of QAW039 (150 mg once daily and 450 mg once daily), compared with placebo in patients with moderate-to-severe asthma receiving SoC asthma therapy.

As this study has been early terminated, the primary endpoint will be analyzed in the way of combined treatment period 1 and treatment period 2. Treatment emergent AEs are defined as adverse events (including asthma exacerbations), starting on or after the day of the first intake of study drug in this study and until the earlier date out of: date of last intake of study drug +7 days (30 days in the case of a serious AE) and final visit.

Any AEs that started during the study after informed consent and before the time of the first intake of study drug will be classified as a prior AE and not classified as treatment emergent AE. The time-to-first treatment emergent AE is defined as the time to the occurrence of an AE from the treatment start date, and computed as time to AE=AE start date – treatment start date +1 day. As a general rule of censoring, patients who either completed the study or discontinued

treatment prematurely or continued treatment and without the event of interest will be censored at the minimum out of the dates of last medication intake + 30 days, final visit date, and date of death. Time-to-first treatment emergent SAEs and time-to-first treatment emergent AEs leading to discontinuation from study treatment are defined in a similar manner as time-to-first treatment emergent AE.

The definition and rationale for the estimand for the primary endpoint are given in [Table 2-1](#). The statistical strategy to handle each intercurrent event is described in more detail in [Section 2.5.3](#).

Table 2-1 Summary of estimand for the primary endpoint

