Population		Justification	

Male or female patients aged 12 years and older with moderate-to-severe asthma on standard-of-care asthma therapy and receive at least one dose of study treatment, including two categories of patients:
 
 • Rollover patients: patients completing a prior Phase 3 study (A2307, A2314, A2316, or A2317) of fevipirant; and • New patients: patients with inadequately controlled asthma who had not previously participated in a study of fevipirant. 		
Fevipirant (QAW039) is a Prostaglandin D2 receptor 2 (DP2) antagonist expected to provide benefit in asthma by impacting major effector cells and soluble factors driving airway inflammation in asthma. Treatment with fevipirant should result in a decrease in these parameters of airway inflammation as well as a clinical improvement in asthma.
	
Variables		Justification	

 • Time-to-first treatment emergent AEs • Time-to-first treatment emergent SAEs and • Time-to-first treatment emergent AE leading to discontinuation from study treatment. 		
The primary endpoints provide safety assessments with respect to the timing of first occurrence of treatment emergent AEs, SAEs, and AEs leading to study treatment discontinuation.
	
Intercurrent event	Description	Strategy to handle event	Justification
Discontinuation of fevipirant for any reason without experiencing a safety outcome as defined in the primary variables	Discontinuation of fevipirant for any reason regardless of relation to fevipirant without experiencing a safety outcome as defined in the primary variables	A hypothetical strategy will be used assuming a continued risk for a first event after study treatment discontinuation as described in Section 2.5.3	
These patients may discontinue therapy in clinical practice. Any fevipirant treatment effect would cease almost instantly after discontinuation of fevipirant, and only SoC effect is expected.
 
The safety outcomes would be no more or less likely to occur after discontinuation of fevipirant.

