Ascending Kaplan-Meier curves will be constructed by treatment arm on overall population and by source of patients. The number of subjects with an event, number of subjects remaining at risk in the treatment group, estimate of the event rate and its estimated standard error, as estimable, will be provided for each treatment group. Median time to event and quartiles including 95% confidence intervals will be summarized as well.

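### For AEs leading to discontinuation, the SAP's ascending Kaplan-Meier curves lie above the cumulative incidence that the protocol says will be displayed, because stopping for other reasons and death are competing events (minor; display and absolute-risk estimates only)

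*SAP*

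**What the plan says.** Protocol 9.4.2, in the summary statistics for the primary variable, states: "Estimates of the cumulative incidence of the primary outcomes will be displayed graphically for the SAF". It does not name an estimator. SAP 2.5.2 specifies the display: "Ascending Kaplan-Meier curves will be constructed by treatment arm on overall population and by source of patients". It also tabulates an event-rate estimate with its standard error for each treatment group.

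One of the three primary variables in SAP 2.5.1 is "Time-to-first treatment emergent AE leading to discontinuation from study treatment". The general censoring rule there covers patients who complete or stop treatment early. Those "without the event of interest will be censored at the minimum out of the dates of last medication intake + 30 days", the final visit and death, whichever comes first. The third variable follows the same pattern as the first.

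SAP Table 2-1 handles stopping QAW039 without the event as follows: "A hypothetical strategy will be used assuming a continued risk for a first event after study treatment discontinuation as described in Section 2.5.3". Placebo is treated in parallel. The only summary measure in that table is the hazard ratio. SAP 2.5.3 states the independent-censoring assumption for the Cox model.

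No competing-risk estimator appears in the readable text of either document, and the readable part of SAP section 4 does not list the display as a change.

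**The concern.** For AEs and SAEs in general, a patient off drug can still fall ill, so a continued risk after stopping is a meaningful idea. For discontinuation because of an AE it is not: someone who has already stopped for another reason, or has died, has no drug left to stop. These are competing events rather than missing follow-up. Censoring them makes the ascending Kaplan-Meier curve an estimate of risk in a setting where no other stopping occurs.

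What is at stake is the absolute risk read from the curves and the tabulated event rates for this variable. In a placebo-controlled safety study, that figure is likely to be quoted as the share of patients who stop because of an AE. The Cox model gives a cause-specific hazard ratio and does not depend on this choice.

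**Working it through.** **Inputs (Protocol 9.8, repeated in SAP section 3).**
- Placebo event rate: Table 9-1 gives 0.03 per patient-year for "Rate of AEs leading to study treatment discontinuation" in every source group.
- Effect: the power statement applies "if both QAW039 doses have a 50% relative hazard increase for treatment emergent events, compared with placebo", so the QAW039 rate is 0.03 × 1.5 = 0.045.
- Censoring: "an exponential censoring rate in the placebo group of 0.22 and of 0.16 in the QAW039 treatment groups". The rate is not split by reason.
- Follow-up T: 1 year (Period 1) and 3 years (Periods 1 and 2).
- 1,570 patients at 3:3:1, or about 224.3 on placebo and 672.9 on each dose.

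**Step 1: reproduce the plan's power.** Write l for the event rate and c for the censoring rate. Expected events are n × l/(l+c) × (1 − exp(−(l+c)T)). Pairwise power is Φ(ln 1.5 / √(1/eP + 1/eQ) − 1.96).
- Period 1: 5.95 placebo events and 27.38 per dose give 14.4%, against a stated 16%.
- Periods 1 and 2: 14.20 and 67.85 events give 28.4%, against a stated 29% and 28%.
- A 10,000-run unstratified Cox simulation with profile-likelihood intervals gives, for 150 mg, 450 mg, both and one of the two, 16/16/10/23% in Period 1 (stated 16/16/9/22%). For Periods 1 and 2 it gives 31/31/21/41% (stated 29/28/19/38%).

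The agreement is close enough to show that the rates are read as the plan uses them.

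**Step 2: compare the two estimators**, first taking all of c as competing stops.
- 1 minus Kaplan-Meier: 1 − exp(−lT). Placebo at 3 years: 1 − exp(−0.09) = 8.61%.
- Cumulative incidence: l/(l+c) × (1 − exp(−(l+c)T)). Placebo at 3 years: (0.03/0.25) × (1 − exp(−0.75)) = 6.33%.
- QAW039 at 3 years: 1 − exp(−0.135) = 12.63%, and (0.045/0.205) × (1 − exp(−0.615)) = 10.08%.

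| Time | Arm | 1 − KM | Cumulative incidence | Excess (points) | Factor |
|---|---|---|---|---|---|
| 1 year | Placebo | 2.96% | 2.65% | 0.30 | 1.11 |
| 1 year | QAW039 | 4.40% | 4.07% | 0.33 | 1.08 |
| 3 years | Placebo | 8.61% | 6.33% | 2.28 | 1.36 |
| 3 years | QAW039 | 12.63% | 10.08% | 2.54 | 1.25 |

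(Excesses are taken from unrounded values.) At 3 years the risk ratio is 12.63/8.61 = 1.47 by Kaplan-Meier and 10.08/6.33 = 1.59 by cumulative incidence. The risk difference is 4.02 against 3.75 points.

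**Step 3: vary the competing share of c.** The remainder is treated as censoring that both estimators handle alike. Three-year results at hazard ratio 1.5:

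| Share competing | Placebo incidence (factor) | QAW039 incidence (factor) |
|---|---|---|
| 25% | 7.94% (1.08) | 11.92% (1.06) |
| 50% | 7.35% (1.17) | 11.26% (1.12) |
| 75% | 6.81% (1.26) | 10.65% (1.19) |

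**Step 4: the 30-day extension.** Under the SAP rule, patients stay in the risk set for up to 30 days after a stop that already rules out the event. Three-year 1 minus Kaplan-Meier becomes 8.46% on placebo and 12.48% on QAW039, still above 6.33% and 10.08%.

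**Step 5: no treatment effect.** At hazard ratio 1.0, three-year Kaplan-Meier gives 8.61% in both arms. Cumulative incidence gives 6.33% on placebo and (0.03/0.19) × (1 − exp(−0.57)) = 6.86% on QAW039.

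**The case against.** The strongest reply is that the SAP chose its target. Under a hypothetical strategy with independent censoring, 1 minus Kaplan-Meier is a coherent estimate of the risk without other stopping. It also shows no arm difference when the hazards are equal, whereas cumulative incidence shows 6.9% against 6.3% (Step 5). This stands as a caution about reading cumulative incidence alone. It does not settle the display: Table 2-1 names only hazard ratios as its measure, its continued-risk premise does not fit a patient already off drug, and nothing labels the curves as hypothetical.

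Other parts of the reply also have force. The protocol names no estimator, and ascending Kaplan-Meier curves are often offered as cumulative incidence. SAP 2.8.1 separately gives counts and exposure-adjusted rates for AEs leading to permanent discontinuation, though these do not give risk over time. With about 224 placebo patients, the Kaplan-Meier standard error at plan rates is about 1.2 points at 1 year and 2.2 at 3 years, so the one-year gap is well inside the noise. Protocol 9.4.4 and parts of SAP section 4 are blacked out. The SAP says the supportive analyses of 9.4.4 move to the exposure incidence rate summaries, so a competing-risk curve there looks unlikely, but it cannot be excluded.

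A reader might infer three stronger points that the documents do not support:
- That the plan expects other-cause stopping to differ by arm. It states total censoring rates of 0.22 and 0.16 without a breakdown.
- That the overstatement is simply larger on placebo. That holds for the ratio (1.36 against 1.25). In points, at hazard ratio 1.5, it is slightly larger on QAW039 (2.54 against 2.28), and Kaplan-Meier slightly enlarges the risk difference.
- That the primary comparison is biased. The hazard ratios, their intervals and the power figures do not change.

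**Conclusion.** The point holds for the third primary variable only, and it is minor: it affects the curves and the tabulated event rates. For that variable, 1 minus Kaplan-Meier lies above the cumulative incidence whenever anyone stops for another reason or dies.

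The upper end of the size is an excess of 2.3 points on placebo and 2.5 on QAW039 at 3 years. It rests on the planning rates, a hazard ratio of 1.5, constant hazards and all censoring being competing stops. With 25% to 75% of the censoring competing, the three-year factors are 1.08 to 1.26 on placebo and 1.06 to 1.19 on QAW039. SAP 2.5.1 records that the study was terminated early. That shortens follow-up and adds administrative censoring, which both estimators treat alike, so the smaller values are more likely.

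**What to change.** In SAP 2.5.2, for the third primary variable, present the Aalen-Johansen cumulative incidence by arm. Treat stopping study treatment for any other reason, and death, as competing events. Censor only patients still on drug at completion or at sponsor termination. Show the incidence of the competing event beside it, and keep the Cox hazard ratio as planned. If the Kaplan-Meier curve is also shown, label it as the hypothetical risk with no other discontinuation. Record the choice in SAP section 4.

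The data are already collected: Protocol 5.6.2 requires the primary reason for stopping treatment on the Dosage Administration eCRF. The cost is one SAP sentence and a standard procedure. The displayed risks become lower and will also reflect any arm difference in other-cause stopping, which is why they should be read with the hazard ratio.

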2.5.3 Handling of missing values/censoring/discontinuations

The primary Cox regression model will implicitly impute the censored data under the assumption of independent censoring (conditional on the baseline covariates). That is, a censored patient is assumed to be no more or less likely to experience an event in any future

time interval than other patients in the same stratum that continue to be at risk for a first event and that have the same model covariates. The implied assumption of a continued treatment effect after treatment discontinuation is considered conservative for the purpose of the evaluation of safety outcomes that are assumed to be more likely to occur while active treatment is ongoing.

2.6 Analysis of the key secondary objective

The study does not have any key secondary objectives.

2.7 Analysis of secondary efficacy objective(s)

The secondary objectives of the study are based on safety variables and hence no efficacy variables are stated in this section.

2.8 Safety analyses

The primary and secondary objectives of the study are based on safety variables. All safety data will be summarized for the SAF.

2.8.1 Adverse events (AEs)

Adverse events after informed consent including asthma exacerbations will be recorded. Adverse events that started during the study after informed consent and before the day of the first intake of study drug will be classified as prior adverse events and not included in tabulations of treatment emergent adverse events.

The following treatment emergent AE summaries will be produced by system organ class (SOC), preferred term (PT), treatment on overall population, by source of patients for:

1. all AEs,
2. all AEs by maximum severity,
3. suspected drug-related AEs,
4. AEs by standardized MedDRA query (SMQ) level
5. SAEs, and
6. AEs leading to permanent discontinuation of study-drug.

The number of patients experiencing an event, as well as the exposure-adjusted incidence rate (patients with events per 100 patient year of follow-up) will be provided in above summaries. Patient year of follow-up will be computed as (sum of the duration of exposure over patients, in days)/365.25. This method will account for the length of follow-up time under the assumption that events would occur with the same frequency at any point in time.

Summaries described above will also be produced by source of patients.

Post-treatment discontinuation AEs (events that start more than 7 days (30 days in the case of a serious AE) after the last intake of study drug) will be summarized separately in terms of number and percentage of patients with at least one AE.

Secondary endpoint: the rate of patients with at least one treatment emergent AE by primary system organ class

The number and proportion of patients with at least one treatment emergent AE by primary system organ class will be presented descriptively and analyzed using a logistic regression model stratified by randomization stratum (but not by region) and treatment group, severity of asthma (GINA treatment step 3, 4, and 5), and region as fixed class effects. Estimates of the odds ratios between QAW039 groups and placebo will be displayed along with associated 95% confidence intervals. Firth's penalized likelihood will be utilized for logistic regression for rare events.

Secondary endpoint: the rate of treatment emergent severe asthma exacerbation episodes requiring hospitalizations

In safety analysis, each record of asthma exacerbation episode will be considered as an adverse event regardless of the interval between two episodes, i.e., no collapsing of multiple records (this differs from how asthma exacerbations are included in efficacy analyses – see Section 2.13.1). Number of treatment emergent severe asthma exacerbation episodes requiring hospitalizations (any visit to the hospital requiring an overnight stay or an emergency room visit greater than 24 hours) will be summarized by source of patients.

Adverse events of special interest / grouping of AEs

AEs of special interest definitions are found in the compound electronic Case Retrieval Strategy (eCRS). The classification reflects the current version of the dSPP and might be updated based on review of accumulating data. To identify AEs of special interest at the time of the final analysis, the latest version of the eCRS where Core safety topic risk (SP) = 'Yes' or Other Search risk (OS) = 'Yes' will be used.

The number and percentage of patients with treatment emergent AEs of special interest will be summarized by risk category, PT, treatment on overall population and by source of patients. In addition, summaries will be provided for

- Treatment emergent AEs of special interest by maximum severity
- Treatment emergent serious AEs of special interest
- Treatment emergent AEs of special interest that are suspected to be related to study drug

AE reporting for CT.gov and EudraCT

For the legal requirements of clinicaltrials.gov and EudraCT, two required tables on treatment emergent adverse events which are not serious adverse events with an incidence greater than X% and on treatment emergent serious adverse events and SAE suspected to be related to study treatment will be provided by system organ class and preferred term on the safety set population.

If for a same patient, several consecutive AEs (irrespective of study treatment causality, seriousness and severity) occurred with the same SOC and PT:

- a single occurrence will be counted if there is ≤ 1 day gap between the end date of the preceding AE and the start date of the consecutive AE
- more than one occurrence will be counted if there is > 1 day gap between the end date of the preceding AE and the start date of the consecutive AE

For occurrence, the presence of at least one SAE / SAE suspected to be related to study treatment / non SAE has to be checked in a block e.g., among AE's in a ≤ 1 day gap block, if at least one SAE is occurring, then one occurrence is calculated for that SAE.

The number of deaths resulting from SAEs suspected to be related to study treatment and SAEs irrespective of study treatment relationship will be provided by SOC and PT.

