9.5.2 Safety variables

All safety data will be summarized for the SAF.

Safety summaries will be primarily based on on-treatment data with selected tables also presented for the all data after the first intake of study drug, while all data based safety data will be listed.

Secondary safety endpoints

The secondary endpoint of the rate of patients with at least one treatment emergent AE by primary system organ class will be presented descriptively and analyzed using a Cox regression model in a similar manner as the primary endpoint. A supportive analysis on the rate of patients with at least one AE by primary system organ class will be conducted similarly including all AEs starting on or after the time of the first intake of study drug (i.e., treatment emergent AEs and AEs occurring during the post-treatment follow-up).

The secondary endpoint of the rate of treatment emergent patient deaths and patient hospitalizations (any visit to the hospital requiring an overnight stay or an emergency room visit greater than 24 hours) due to an asthma exacerbation will be analyzed using a negative binomial regression model. The model will include randomization stratum (as in the analysis on primary endpoint), treatment group, severity of asthma (GINA steps 3, 4 and 5), and region as fixed class effects, with the natural logarithm of the duration of on-treatment follow-up in years as an offset variable. The duration of on-treatment follow-up in years will be calculated

for each patient as (treatment end date - treatment start date + 2 days)/365.25 without taking into account treatment interruptions. A supportive analysis of the rate of patient deaths and patient hospitalizations due to asthma exacerbations treatment emergent and after treatment discontinuation will be conducted similarly with the natural logarithm of the duration of follow-up in years as an offset variable.

In addition to the inferential analysis, summary statistics on the secondary safety variables will be presented as described below.

Adverse events

Adverse events after informed consent including asthma exacerbations will be summarized and listed. Summaries will include the number of patients with an event, exposure-adjusted incidence rates (patients with an event per patient year of follow-up to first event or censoring) and the percentage of patients with an event.

The following treatment emergent AE summaries will be produced:

- overall by system organ class and preferred term,

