2.4 Treatments (study treatment, rescue medication, concomitant therapies, compliance)

2.4.1 Study treatment / compliance

The duration of exposure, the number of patients randomized who completed the foreseen course of study medication and the number of patients who discontinued from the study medication will be summarized on overall population, by source of patients, by source of patients and prior treatment in a prior Phase 3 study. Since the study has a double dummy design each patient will be dispensed two bottles of study medication at the dispensing visits. Bottle 1 has study medication corresponding to 150 mg QAW039 or placebo and Bottle 2 has study medication corresponding to 450 mg QAW039 or placebo. Exposure and compliance will be presented on the SAF. Exposure will be presented for each treatment while compliance will be presented by treatment arm for each of the bottles separately.

Duration of exposure to a treatment will be calculated as the number of days between the first dose date and the last dose date exposed to that treatment over the specified period (expressed as: Duration of exposure = Date of last known dose of study drug – Date of first dose of study drug + 1). In addition, the duration of exposure will be summarized as a categorical variable classified into <4 weeks, ≥ 4 – <12 weeks, ≥ 12 – <26 weeks, ≥ 26 – <52 weeks, ≥ 52 – <104 weeks, ≥ 104 – <156 weeks, ≥ 156 weeks.

Patients in the randomized set who received any wrong study medications will be identified using the information recorded on the DAR page of the eCRF. If there is a record with reason = dispensing error, then the pack number will be used to identify whether or not the patient received the wrong study drug.

Study compliance will be calculated as the percentage of days with study medication intake (taking into account the duration of the drug interruptions) during the period from first intake to last intake.

Study compliance = $100 \times \text{number of days with study medication intake as per protocol} / (\text{Day of the last treatment} - \text{Day 1} + 1)$.

Compliance will be categorized as <80%, 80% -100%, and summarized by treatment arm and source of patients for each of the bottles separately based on the SAF.

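### SAP 2.8.1 divides a once-per-patient event count by total exposure, so the descriptive rates for common AE rows fall as follow-up lengthens and flatten between arms

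*SAP*

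**What the plan says.** **SAP 2.8.1.** The AE tables by system organ class (SOC) and preferred term (PT), overall and by source of patients, give patients with events per 100 patient-years. The denominator is: "Patient year of follow-up will be computed as (sum of the duration of exposure over patients, in days)/365.25". The justification assumes an event frequency that is constant over time: "This method will account for the length of follow-up time under the assumption that events would occur with the same frequency".

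**SAP 2.4.1.** Exposure runs from first to last dose ("Duration of exposure = Date of last known dose of study drug" minus the first dose date, plus 1). It does not stop at an event.

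**Protocol 9.5.2.** The same kind of rate is "patients with an event per patient year of follow-up to first event or censoring". Protocol 9.4.2 agrees for the primary variables: "patients with treatment emergent AEs per patient year of follow-up to first event [AE or censoring". The same paragraph of 9.4.2 also gives a whole-duration formula, "treatment end date - treatment start date + 2 days)/365.25 without taking into account treatment interruptions", without saying how the two fit together.

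**Event window and censoring.** SAP 2.5.1 counts events up to the earlier of "date of last intake of study drug +7 days (30 days in the case of a serious AE) and final visit". Its time-to-event censoring rule is different: patients without an event are "censored at the minimum out of the dates of last medication intake + 30 days, final visit date, and date of death". Protocol 9.4.3 censors on the day after the last intake.

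**The concern.** A patient who has had a first event cannot add to the numerator again, yet under SAP 2.8.1 continues to add to the denominator. The rate therefore mixes the hazard with the length of follow-up. It looks adjusted for exposure, but for common rows it is not.

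This matters because safety is the study's only primary and secondary purpose. SAP 2.5.1 says the study was terminated early, and the tables are split by source of patients, so unequal follow-up is plausible. The secondary SOC objective is worded as a rate, but the SAP analyses it with counts, proportions and odds ratios, none of which adjusts for follow-up. This rate is thus the only visible SOC/PT summary that sets out to adjust for exposure. SAP section 4 also moves the supportive analyses of protocol 9.4.4 (not visible) onto these rate summaries.

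Separately, the numerator runs 7 days (30 for SAEs) past the last dose while the denominator stops at the last dose.

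**Working it through.** **Inputs.** From SAP section 3: placebo rates per patient-year of 2.86 (any AE) and 0.24 (SAE), outside A2316/A2317; hazard ratio 1.5; exponential dropout 0.22 on placebo and 0.16 on QAW039. The documents give no SOC/PT rates and no achieved follow-up. Row rates of 1, 0.5 and 0.1 per patient-year, and follow-up uniform on 0.25 to 2 years, are assumptions.

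**Plan's own figures.** No incidence rate is stated, so the check on the inputs is the power table (SAP Table 3-2). Simulated stratified Cox models with profile-likelihood intervals, assuming 600 of the 1000 rollovers come from A2307/A2314, gave for one of the two doses over both periods 95.2% for SAEs (table 94) and 39.4% for discontinuation AEs (table 38). The inputs reproduce the table within simulation error.

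**Formulas.** For event rate l, dropout c and follow-up T:
- probability of an event, P = l/(l+c) × (1 − exp(−(l+c)T))
- mean total exposure, E = (1 − exp(−cT))/c
- mean time to first event or censoring, F = (1 − exp(−(l+c)T))/(l+c)
- SAP rate = P/E; rate to first event = P/F = l for every T.

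**Any AE, placebo, T = 1.** P = 2.86/3.08 × (1 − exp(−3.08)) = 0.886. E = (1 − exp(−0.22))/0.22 = 0.898. The SAP rate is 0.886/0.898 = 98.7 per 100 patient-years. F = 0.310, so the first-event rate is 0.886/0.310 = 286.

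**Constant hazard, SAP rate per 100 patient-years**

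| Row | 0.5 y | 1 y | 2 y | 3 y | True |
|---|---|---|---|---|---|
| Any AE, placebo | 154.1 | 98.7 | 57.3 | 42.3 | 286 |
| Any AE, QAW039 | 178.9 | 103.1 | 56.3 | 40.5 | 429 |
| 0.5 per PY, placebo | 44.3 | 39.7 | 32.8 | 28.0 | 50 |
| SAE, placebo | 22.6 | 21.4 | 19.4 | 17.8 | 24 |
| 0.03 per PY, placebo | 3.0 | 3.0 | 2.9 | 2.9 | 3.0 |

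For the 0.5 row, a source of patients followed for 0.5 year looks 35% higher than one followed for 2 years (44.3/32.8 = 1.35) at the same hazard.

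**Between arms, follow-up 0.25 to 2 years, true ratio 1.50** (numerator and denominator each averaged over T)

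| Row | Placebo | QAW039 | SAP ratio | Ratio, dropout 0.16 in both arms |
|---|---|---|---|---|
| 1 per PY | 58.5 | 70.1 | 1.20 | 1.21 |
| 0.5 per PY | 37.4 | 49.0 | 1.31 | 1.32 |
| 0.1 per PY | 9.4 | 13.7 | 1.45 | 1.46 |

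The last column shows that the flattening does not come from unequal dropout.

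**Window mismatch.** With the full 30 days after the last dose in the SAE numerator and the hazard continuing off drug, the SAE rate reads 26.3 vs 38.1 at 0.5 year (true 24 vs 36) and 23.2 vs 32.7 at 1 year. Overstatement appears only at the shorter follow-up.

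**Choice of replacement denominator** (simulation, non-serious row at 0.1 per PY, 0.5 year, true 10 vs 15)
- SAP method with the 7-day window: 10.2 vs 15.0
- Time to first event, event-free time to last dose + 30 days: 8.9 vs 13.4
- Time to first event, event-free time to last dose + 7 days: 10.0 vs 15.0

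For any AE, which mixes serious and non-serious events, stopping event-free time at + 7 days gives about 287 vs 430 (true 286 vs 429).

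**The case against.** **The rate is only descriptive.** This stands. No test, interval or between-arm ratio of it is visibly planned, and any AE, SAE and discontinuation AE have Cox and Kaplan-Meier analyses on time to first event. A reader might infer that the study's main safety conclusions are compromised; the documents do not support that.

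**The most striking figures need extreme settings.** Also fair. The any-AE ratio falls below 1 (40.5/42.3 = 0.96) only with about 2 to 3 years of follow-up for everyone and longer exposure on active drug, in a study stopped early. The row at 1 per patient-year means about 57% of placebo patients have an event in that row. The hazard ratio of 1.5 in each row is also assumed.

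**The protocol is not clean either.** Protocol 9.4.2 places a whole-duration formula beside the rate, so the SAP may have followed that formula. But both protocol sections word the rate itself on follow-up to first event, and 9.5.2 has no competing formula. A reader might infer an undeclared protocol departure. The visible bullets of SAP section 4 do not mention the denominator, but some bullets are blacked out, so this cannot be settled.

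**SAE overstatement.** A reader might infer that SAE rates are generally too high. That requires short follow-up and most patients having the full 30 days before the final visit, which also caps the window and is not defined in the visible text. With no post-dose window, the 0.5-year placebo rate reads 22.6, below the true 24.

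**An obvious repair can do harm.** Borrowing the single + 30-day censoring date of SAP 2.5.1 lowers non-serious rates by about 5% at 1 year and 10% at 0.5 year. For rare rows that is worse than the SAP method.

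**Conclusion.** The concern holds for the descriptive rates. The denominator does not match the once-per-patient numerator or the protocol's wording of the rate, and the SAP's reason for it is mathematically incorrect. Common AE and SOC rows are understated, flattened between arms, and not comparable between sources of patients whose follow-up differs.

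The size depends on how common the row is: a true ratio of 1.50 reads about 1.20, 1.31 and 1.45 at 1, 0.5 and 0.1 per patient-year. This rests on a constant hazard, the plan's hazard ratio and dropout rates, and assumed row rates and 0.25 to 2 years of follow-up. Rare rows are little affected; neither are AEs leading to discontinuation, where exposure ends at about the time of the event. The Cox, Kaplan-Meier and logistic analyses do not use this rate. It should be fixed, because the rule and its justification are wrong as written and the change is cheap.

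**What to change.** - **Denominator, SAP 2.8.1.** For each row, sum the time from first dose to the first qualifying event or, if none, to the end of that row's own treatment-emergent window: the earliest of last dose + 7 days (+ 30 days for SAE rows), final visit and death. Divide by 365.25.
- **Mixed rows.** Where serious and non-serious events are combined, use + 7 days for event-free patients.
- **Do not** apply the single + 30-day censoring date of SAP 2.5.1 to non-serious rows.
- **Delete** the sentence claiming that total exposure accounts for length of follow-up.
- **Declare in SAP section 4** how the rate's censoring differs from the protocol's day after last intake, and that the whole-duration formula in protocol 9.4.2 is not used for this rate.

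Cost: SAP wording and somewhat more programming on dates already collected, with no new data or event rules. The downside is a denominator that differs by row.
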